5. ANALYSIS SET

5.1. SCREENED/RANDOMIZED SUBJECTS

- Screened subjects are defined as all subjects who signed an informed consent; Screen Failure Subjects are defined as all subjects who were screened but not dosed.
- Randomized subjects are defined as all subjects who are assigned a randomization number.

5.2. SAFETY ANALYSIS SET

The safety analysis set will include all subjects who are randomized and have drug exposure. The safety analysis set will be used for all analyses of safety endpoints.

5.3. PHARMACOKINETIC ANALYSIS SET

The PK analysis set will include all subjects who are randomized, dosed with any amount of study drug, and for whom PK data are available with no significant protocol violations or deviations that would significantly affect the PK evaluation of the drug.

Factors that may influence serum SEL-037 concentrations and/or the whole blood rapamycin concentrations (e.g., interruptions in the infusion or changes in the infusion rate) will be reviewed. If an influencing factor is present, a decision will be made by the responsible pharmacokineticist, whether to include or exclude the specific sample or subject. If a whole blood rapamycin concentration sample or a serum SEL-037 concentration sample is the subject of an ongoing investigation at the time of databased lock, the corresponding tables, figures and listings involving that sample may be calculated additionally with the exclusion of the sample in question. All subjects and samples excluded from the analysis will be clearly documented in the study report.

5.4. PHARMACODYNAMIC ANALYSIS SET

The PD analysis set will include will include all subjects who are randomized, receive any amount of study drug, and have at least one post-baseline assessment of sUA is available. Uric acid concentrations will be listed for all subjects in PD analysis set.

All available PD data will be included in the listings; the PD data will be evaluated for protocol violations or deviations that would significantly affect the PD evaluation of the drug. Profiles or individual time points with such violations or deviations will be flagged and may be excluded from summary statistics and the derivation of PD parameters. Examples to treat as the deviations will be but not limited to:

Statistical Analysis Plan

- 1) Dose interruptions in their SEL-037 dose such that only partial doses were delivered - PD profiles may be excluded from summaries and may be used in analyses with actual dose of SEL-037 used if possible
- 2) Dose interruptions in their SEL-110 dose such that only a partial dose of SEL-110 and/or NO DOSE of SEL-037 was administered (since only SEL-037 will cause sUA to be reduced) - the profiles for the treatment period with deviation will be excluded from summaries and may be used for additional analyses without SEL-037 if needed; the data for prior periods will be included
- 3) Subjects who have a dose interruption during SEL-110 administration in the 1st treatment period and so do not ever receive SEL-037 but do have measured sUA values - as above, may be used for additional analyses without SEL-037 if needed post-hoc.

5.5. PROTOCOL DEVIATIONS

All protocol deviations related to study inclusion or exclusion criteria, conduct of the trial, subject management, dosing, and sampling procedures or subject assessment will be listed. The list of protocol deviations will be reviewed by the Sponsor, the medical director at Syneos Health , the study statistician and the study pharmacokineticist and finalized before database lock.

Statistical Analysis Plan

6. GENERAL ASPECTS FOR STATISTICAL ANALYSIS

6.1. GENERAL METHODS

SAS® version 9.3 will be used for all statistical analyses and tabulations.

In general, summaries will present data by treatment/cohort and assessment time where appropriate. Unless stated otherwise, descriptive summaries will include n, mean, standard deviation, median, minimum, and maximum for continuous variables, and n and percent for categorical variables. If there are multiple assessments collected on the same scheduled time within the windows, the average of these assessments will be used. For tabulated safety summaries, only the scheduled assessments will be included in the summary tables.

Data collected at unscheduled visits will be included in the data listings but will not be included in the analyses. The data for the EOS visit at day 140 will be separated from the Early Termination visit data and will be summarized for all the subjects within the defined population who reached this visit. An additional observational visit for subjects with <6 mg/dL uric acid concentration on day 140 (approx. 30 days after last dose) were scheduled at approx. 170 days from 1st dose. The data for the observational visit will be reported and summarized for all subjects participating in this visit. Data for Early Termination visits will be listed with actual day from dose included and will not be summarized. The last result for repeat test at screening visit will be considered as final and will be included in summaries. Previous results will be listed but not summarized.

Adverse events and medical history will be coded according to the most recent Medical Dictionary for Regulatory Activities (MedDRA) version. Prior and concomitant medications will be coded using the most recent WHO Drug Dictionary version.

Derivation of PK parameters will be performed using Phoenix WinNonLin 6.4 or higher on a Windows 7 platform or higher.

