4.3. SAFETY ENDPOINTS

The primary objective of this study is to assess the safety and tolerability of multiple IV infusions of SEL-212. Safety assessments will be based on medical review of adverse event (AE) reports and the results of vital sign measurements, electrocardiograms (ECGs), physical examinations, and clinical laboratory tests. These endpoints will be measured at the time points specified in the protocol in Section 1.1, Schedules of Events. The primary endpoints are frequencies of AEs, serious AEs (SAEs), AEs leading to discontinuation, and ECG and laboratory abnormalities occurring up to 30 days after the last dose of study medication.

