11.4. LABORATORY EVALUATIONS

Laboratory data will be summarized by the type of laboratory test. Normal reference

Statistical Analysis Plan

ranges and markedly abnormal results will be used in the summary of laboratory data. Data will be flagged according to the reference limits (High or Low), if applicable. Descriptive statistics will be calculated for each laboratory analyte at baseline and at each scheduled time point for each dose and treatment. Changes from baseline results will be presented descriptively as well as in pre- versus post-treatment cross tabulations (with classes for below, within, and above normal ranges). A listing of subjects with any laboratory results outside the reference ranges will be provided.

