11.6. ELECTROCARDIOGRAM

The ECG variables that will be analyzed are heart rate, RR interval, PR interval, QRS interval, QT interval, QTcB, and QTcF. The ECG measurements will be summarized at each time point of measurement. The change from baseline will be summarized. Descriptive statistics on actual values and changes from baseline by dose and time will be computed. Plots (mean \pm SEM) on changes from baseline over time will be provided. A listing of abnormal clinically significant evaluations as well as a listing of subjects with abnormal QTcF/QTcB values (>450 , >480 and >500 ms) and of subjects with abnormal QTcF/QTcB changes from baseline (≥ 30 but <60 ; ≥ 60) will be provided.

All important abnormalities from the ECG readings, including changes in T wave morphology and/or the occurrence of U waves versus baseline recordings, will be included in the AE listing.

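### Early Termination values are listed but not tabulated, so six laboratory tests have no tabulated result after the last dose in any subject stopped before dose 5, although that window belongs to the primary safety endpoint

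*SAP*

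**What the plan says.** SAP 6.1 sets four rules that act together:

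- Early Termination: "Data for Early Termination visits will be listed with actual day from dose included and will not be summarized".
- EOS: "The data for the EOS visit at day 140 will be separated from the Early Termination visit data", and it is summarized for those who reach it.
- Safety tables: "For tabulated safety summaries, only the scheduled assessments will be included in the summary tables".
- Unscheduled visits: "Data collected at unscheduled visits will be included in the data listings but will not be included in the analyses".

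SAP 4.3 names the primary endpoints as frequencies of AEs, SAEs, AEs leading to discontinuation, and "ECG and laboratory abnormalities occurring up to 30 days after the last dose of study medication".

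For laboratory data, SAP 11.4 plans statistics by scheduled time point and adds: "Changes from baseline results will be presented descriptively as well as in pre- versus post-treatment cross tabulations". It makes no exception for Early Termination. It also plans a safeguard: "A listing of subjects with any laboratory results outside the reference ranges will be provided".

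For ECG, SAP 11.6 plans summaries by time point. Abnormalities get only listings: "A listing of abnormal clinically significant evaluations as well as a listing of subjects with abnormal QTcF/QTcB values".

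**The concern.** Leaving the study before dose 5 is built into the design. Under Protocol 6.3.1, a subject whose Day 21 serum uric acid misses the criterion receives no further dose and has final assessments about 30 days after the last one. The cohort-closing counts of 5 or 10 stopped subjects show that substantial stopping was expected.

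For some tests that final visit is the only draw after the last dose. If it is left out of the tables, the tables cannot give the abnormality frequency that SAP 4.3 defines. Creatinine and BUN matter most here. They are the only renal tests after screening, because Protocol Tables 9-11 mark eGFR and urinalysis at screening only. Protocol 4.3.2.3 reports one Phase 1 SEL-212 subject with a serious event of acute kidney injury, which the investigator called related and the sponsor not likely related.

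**Working it through.** The plan gives no figure to reproduce. The check is a count of scheduled draws.

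**Inputs**

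- Rows marked only at screening, predose and EOS/Early Termination in all three tables of Protocol 19.4 (Tables 9, 10, 11): creatinine, BUN, total bilirubin, Electrolytes, aPTT, INR. That is 6 rows. Table 9 (Cohorts 1-2) adds total cholesterol, HDL, LDL and triglycerides, 4 more. Hct and Hgb in Table 9 carry the same marks but are not counted, because the CBC is drawn at Day 14.
- Treatment period: typically 28 days (Protocol 6.3.1).
- Final assessment: 30 days after the last dose, ± 2 days in the SEL-110 cohorts (Protocol 6.3.1).
- Baseline: last value before the first infusion in Period 1 (SAP 6.2), so the Period 1 predose draw is not a post-dose value.
- ECG: predose in each period, one at 6 hours in Period 1 only, and EOS/Early Termination (Protocol synopsis; Table 3, footnote 10).

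**Can a stopped subject reach the day-140 row?** The final visit after dose k falls on day 28(k − 1) + 30, which is 30, 58, 86 and 114 for k = 1 to 4, and 142 for k = 5. With every window at its limit, 29(k − 1) + 32 gives 32, 61, 90 and 119 for k = 1 to 4. None is near day 140.

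**Values per subject.** For k = 1 to 4, each laboratory row has (k − 1) predose draws after the first dose plus 1 Early Termination draw, so k are collected and k − 1 tabulated. For k = 5 with EOS attended, 4 + 1 = 5 are collected and 5 tabulated. ECGs after the first dose number 1 + (k − 1) + 1 = k + 1 collected and k tabulated for k = 1 to 4; for k = 5, 1 + 4 + 1 = 6 of 6.

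| Doses received | Lab values after first dose, tabulated / collected | Lab values after last dose, tabulated / collected | ECGs after first dose, tabulated / collected |
|---|---|---|---|
| 1 | 0 / 1 | 0 / 1 | 1 / 2 |
| 2 | 1 / 2 | 0 / 1 | 2 / 3 |
| 3 | 2 / 3 | 0 / 1 | 3 / 4 |
| 4 | 3 / 4 | 0 / 1 | 4 / 5 |
| 5, EOS attended | 5 / 5 | 1 / 1 | 6 / 6 |

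For subjects stopped after doses 2 to 4, the untabulated ECG is the only one after the last dose. After dose 1, the 6-hour ECG remains.

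**Other sources.** The only other draw of these rows is the infusion-reaction kit (Protocol Table 12). It is triggered by an event, so the scheduled-only rule excludes it. The denominator conventions in SAP 15.2.5.2 do not help. If the denominator is subjects with an observation, stopped subjects drop out of the last-visit row. If it is subjects exposed, they count without a value.

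**Illustrative size, under assumptions.** Let f be the share of treated subjects stopped before dose 5, and d the difference in last-visit abnormality rate between them and completers. The all-treated rate is (1 − f)p + f(p + d) = p + fd, while the EOS row shows p. The gap is f × d. With d = 10 points, f = 10%, 25% and 50% give 1, 2.5 and 5 points. The documents supply neither f nor d.

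**The case against.** The strongest reply is that nothing is lost. Early Termination values are listed, out-of-range results have their own listing, and Protocol 11.2.2.6 sends clinically significant findings to the AE tables. An acute kidney injury would appear there, as it did in Phase 1. In small open-label cohorts, medical review of listings is a reasonable tool. This limits the consequence, but a listing is not a frequency. The AE route depends on investigator judgment, and SAP 4.3 names laboratory abnormalities separately from AEs.

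A second reply is that Protocol 6.3.1 gives rule-stopped subjects End of Study assessments, so they might be binned as EOS and not as Early Termination. The SAP does not say which label applies. Since it ties the tabulated EOS to day 140, and these subjects finish by day 119 at the latest, neither label puts them in that row.

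Several narrower points stand:

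- ALT, AST and alkaline phosphatase are drawn at Day 14 in every period, so those liver enzymes stay tabulated after the last dose.
- Phosphate, which Protocol 11.1.6 counts among the electrolytes, has its own row with post-dose draws in the SEL-110 cohorts.
- Protocol 12.8.3 promises statistics at scheduled time points and does not expressly promise to tabulate Early Termination. The statement in SAP 13 that nothing changed is therefore weak evidence of a departure, even though the protocol schedules show EOS and Early Termination as one Day 30 column.
- The missing ECG abnormality frequency also affects completers, and Protocol 12.8.4 likewise plans listings. It is a related gap with a separate cause.
- A subject who receives dose 5 but leaves before EOS has the same laboratory gap.

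**Conclusion.** The concern holds and should be fixed. For six laboratory rows in every cohort, and four lipid rows as well in Cohorts 1-2, no value after the last dose is tabulated for any subject stopped before dose 5. Subjects stopped after dose 1 have no tabulated post-dose value at all. The ECG summaries lose the only post-last-dose ECG of subjects stopped after doses 2 to 4. The ECG abnormality frequency named in SAP 4.3 is not produced, except where a finding is reported as an AE.

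The per-subject count follows directly from the schedules and SAP 6.1. The number of subjects affected is unknown. The cohort-closing counts do not supply it, because they may include subjects who first fail at Period 5 Day 21 and still reach EOS, and Part C states only a total of up to 40. Stopping depends on serum uric acid, and the documents do not say whether stopped subjects differ on these tests, so the direction of any bias is also unknown. The 1 to 5 point range is illustrative only.

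AE and SAE tables, scheduled Day 7, 14 and 21 laboratory tests, vital signs at scheduled visits and the 6-hour Period 1 ECG are not affected.

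**What to change.** Amend SAP 6.1, 11.4 and 11.6:

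1. Base laboratory and ECG abnormality frequencies, and the laboratory pre/post cross-tabulations, on each subject's worst post-baseline value through 30 days after the last dose. Include Early Termination and unscheduled assessments, with infusion-reaction draws flagged.
2. Use treated subjects with any post-baseline value as the denominator, and show the number of assessments per subject beside the count.
3. Add one pooled row for the visit 30 days after the last dose, combining Early Termination and EOS. Splitting it by doses received is optional, because cells will be small.
4. Keep by-visit means on scheduled data only.
5. Record the change in SAP 13.

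The pooled row alone closes the tabulation gap at the last visit. The worst-value count is what the SAP 4.3 endpoint calls for over the whole period.

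The cost is SAP wording and modest reprogramming, since the data are already collected. There are two drawbacks to state in the tables. Some Early Termination visits fall off the nominal day. Worst-value counts also rise with the number of assessments, which differs by doses received and by infusion-reaction sampling.

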6.3.1. Stopping Rules in an Individual Subject or in a Cohort

For this clinical trial a treatment period is defined as period of time from the beginning of dosing of the first study drug on a given dosing day (ie, Either saline placebo or SEL-110 during Part A of the study and SEL-037 during Part B of the study) to the beginning of the next scheduled dose of study drug, and has a typical duration of 28 days.

For Part C (Cohorts 13, 15, and 17), a treatment period is defined as the period of time from the beginning of dosing of SEL-212 to the beginning of the next scheduled dose of study drug.

Individual

For subjects in Cohorts 1 and 2, any subject who has a weekly serum uric acid value ≥ 6 mg/dl or $>50\%$ of their baseline (where baseline value refers to the pre-dose serum uric acid level from visit 4, Day 0, treatment period 1) at Day 21 of their current treatment cycle will not be eligible for the next dosing of SEL-037. The subject will be followed for 30 days post the last dose of study drug at which time they will have an End of Study assessment and their participation in the study will be terminated.

In Cohorts 3-8, 10-13, 15, and 17 only subjects whose ambient blood samples indicate a serum uric acid (sUA) value less than or equal to 1.0 mg/dL at any of the Day 21 visits will be eligible for the next dosing of SEL-212 (or SEL-037). All other subjects will be followed for 30 ± 2 days post the last dose of study drug at which time all of the End of Study assessments will be completed and their participation in the study will be terminated.

Cohort

If 5 subjects in any of Cohorts 1-5 or 7, or if 10 subjects in any of Cohorts 6, 8, 10, 11, or 12 have met the requirements for individual stopping of their participation in the trial as described above or have been stopped based on Section 6.4 then that cohort will no longer have any additional subjects enrolled in it. Those subjects who have been enrolled will continue until they fulfill the requirements

Study: SEL-212/201 Version: 7.1	Effective Date March 19, 2018
------------------------------------	----------------------------------

for individual stopping or complete the clinical trial treatment periods. If they continue to meet the requirements for continued participation they may continue in Part B of the study.

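### Laboratory and ECG abnormality frequencies are primary endpoints, yet SAP 6.1 keeps Early Termination and unscheduled values out of the safety tables

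*SAP*

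**What the plan says.** SAP 4.3 sets the endpoint: "The primary endpoints are frequencies of AEs, serious AEs (SAEs), AEs leading to discontinuation, and ECG and laboratory abnormalities occurring up to 30 days". The 30 days run from the final administration of study drug.

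SAP 6.1 then fixes which records reach the tables:

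- The general rule on record selection reads: "For tabulated safety summaries, only the scheduled assessments will be included in the summary tables".
- The final visit of completers is kept apart: "The data for the EOS visit at day 140 will be separated from the Early Termination visit data". Only the former is summarized, for subjects who reached it.
- The rule for those who stop early is: "Data for Early Termination visits will be listed with actual day from dose included and will not be summarized".
- Visits outside the schedule are treated in a similar way: "Data collected at unscheduled visits will be included in the data listings but will not be included in the analyses".
- Repeats at one time point are merged: "If there are multiple assessments collected on the same scheduled time within the windows, the average of these assessments will be used".

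SAP 11.4 plans laboratory descriptive statistics by time point, a cross-tabulation of pre- against post-treatment range class, and a listing of out-of-range results. It does not say which post-treatment value enters the cross-tabulation. SAP 11.5 plans vital sign statistics by time point. SAP 11.6 plans ECG descriptive statistics and listings of QTc outliers. None of these sections exempts abnormality frequencies from 6.1 or gives a worst-value rule. SAP 15.2.5.2 makes the default percentage denominator the subjects who have an observation.

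Protocol 6.3.1 stops dosing when the Day 21 serum uric acid (sUA) criterion is not met. In the SEL-212 cohorts follow-up then runs to 30 ± 2 days from the final administration. The protocol says of that visit: "at which time all of the End of Study assessments will be completed and their participation in the study will be terminated". Cohorts 1 and 2 have a similar rule at 30 days. Under Protocol 7.4.2 a completer is a subject who has reached Day 30 of Treatment Period 5.

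**The concern.** The endpoint covers the whole period to about 30 days after the last dose. For anyone who stops early, that period closes with a visit that 6.1 gives no place in the tables. Early stopping is built into this design through the sUA rule, so the exclusion is not confined to a few withdrawals.

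Several safety tests are scheduled so sparsely that the closing visit is the only look after the last dose. If that value is not tabulated, an abnormality first seen there does not enter the primary frequency. The affected subjects are mainly those who lost the sUA response, so the tables would describe continuing subjects better than stopped ones.

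**Working it through.** The documents give no figure to reproduce. The check counts scheduled values per subject and asks how many reach the tables.

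**Inputs.** Protocol 19.4, Tables 9 to 11: aPTT, INR, electrolytes, total bilirubin, BUN and creatinine are marked at screening, at predose of each period and at EOS/Early Termination, with nothing at Day 7, 14 or 21. Protocol Synopsis, safety criteria: ECG at predose in every period, at 6 hours in Period 1 only, and at the final visit. Dosing is every 28 days.

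**Formulas, for a subject who receives k doses:**

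- Six laboratory tests, values after the first dose: (k − 1) predose + 1 final = k. Tabulated: k − 1 if stopped (k < 5), 5 if completed.
- ECGs after the first dose: 1 at 6 hours + (k − 1) predose + 1 final = k + 1. Tabulated: k if stopped, 6 if completed.
- Nominal day of the final visit: 28(k − 1) + 30.

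| Doses | Six tests, tabulated/taken | ECG, tabulated/taken | Final visit, day |
|---|---|---|---|
| 1 | 0/1 | 1/2 | 30 |
| 2 | 1/2 | 2/3 | 58 |
| 3 | 2/3 | 3/4 | 86 |
| 4 | 3/4 | 4/5 | 114 |
| 5 (completer) | 5/5 | 6/6 | 142 |

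The predose values of periods 2 to k all precede the last dose. A stopped subject therefore has no tabulated value after the last dose for the six tests. For ECG, only the 6-hour recording after a single dose survives. Day 142 corresponds to the SAP's day 140 visit; the other final visits fall well before it.

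**Direction of the count.** Over the same days, a count of subjects with at least one abnormal value among some of their records cannot exceed the count among all of them. Averaging does not reverse this, because two in-range values cannot average out of range. The argument does not extend to middle bands such as a QTc change of at least 30 but below 60 ms, because an added value can move a subject out of the band.

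**Direction of the percentage.** Assumed example: 20 subjects, 10 stopped after dose 1, and 1 abnormal creatinine among the 10 who continue. The stopped subjects have no tabulated post-dose value and leave the denominator, so the plan gives 1/10 = 10%. With all records the result is (1 + 2)/20 = 15% if 2 stopped subjects are abnormal, and 1/20 = 5% if none is.

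**Scale.** The number of stopped subjects is not stated. The cohort rule shows only what the design allows for: "If 5 subjects in any of Cohorts 1-5 or 7, or if 10 subjects in any of Cohorts 6, 8, 10, 11, or 12" meet the individual stopping rule or are stopped under Protocol 6.4, enrolment in that cohort closes. Five is 25% of a cohort of 20 and 83% of a cohort of 6; ten is 50% of a cohort of 20. Suppose each stopped subject has a chance q, assumed 5% to 30%, that the only abnormality is at the closing visit. Expected missed subjects are n × q: 0.25 to 1.5 for n = 5, and 0.5 to 3.0 for n = 10. The chance of missing at least one, 1 − (1 − q)^n, is 23% to 83% and 40% to 97%. The documents give no value of q.

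**The case against.** **The visit may not be an Early Termination visit.** Protocol 7.4.3.1 describes early termination as withdrawal of consent or termination by the Investigator, and 6.3.1 calls the stopped subject's closing assessments End of Study. Classing these subjects as Early Termination is an inference. It makes little difference: 6.1 summarizes an End of Study visit only at day 140, and a final visit near Day 30, 58, 86 or 114 has no summarized slot under either reading.

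**No any-abnormal table is planned.** This stands. SAP 11.4 and 11.6 define no such table; the subject-level abnormality outputs are listings, which do include these values. The count is therefore the one that 4.3 implies. But 4.3 calls frequencies primary, and whatever table is built must follow 6.1.

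**A reader might infer that the primary count can only be too low.** The documents do not support that. The End of Study visit has a ± 1 day window, so a Day 31 abnormality would be tabulated although it lies outside a literal 30 days. A stopped subject's visit on Day 31 or 32 lies outside it too, so omitting that visit is not strictly an undercount. Nor do the documents link loss of sUA response to abnormal coagulation, renal or QTc results, so a safety bias in a known direction is not shown.

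**The main laboratory risks are covered.** This largely stands. The SEL-110 risks named in Protocol 4.4.2 (white cells, glucose, lipids, phosphate) are also drawn on Days 7, 14 and 21 in Periods 1 to 3 of the SEL-212 cohorts and throughout Part C. ALT, AST and alkaline phosphatase have a Day 14 draw. The gap concerns the six tests and ECG.

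**Mitigation.** Findings the investigator judges clinically significant become adverse events (Protocol 11.2.2.6) and are tabulated as such. That depends on judgment and does not give the abnormality frequency.

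**Conclusion.** The point holds as a conflict between two SAP rules: 4.3 defines a primary frequency to about 30 days after the last dose, and 6.1 keeps from the tables the visit that closes that window for subjects stopped early. The loss per stopped subject is exact: every post-last-dose value of six laboratory tests, and every post-last-dose ECG from the second dose on. The effect on reported results is unknown in size. For percentages it is also unknown in direction.

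This rests on two assumptions: that 6.1 is applied as written to the tables that serve 4.3, and that a stopped subject's closing visit is not moved into the day 140 slot. Infusion-reaction laboratory samples (Protocol Table 12) may be lost in the same way, but the SAP does not say whether they count as scheduled. Averaging of repeats is a minor matter, since laboratory tests and ECGs are planned once per time point.

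The change is worth making before database lock. It does not call the collection of safety data into question.

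**What to change.** In SAP 6.1, confine averaging, scheduled-only selection and the Early Termination exclusion to continuous by-time-point statistics, where they are reasonable. Then add wording such as:

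*Subject-level counts of laboratory and ECG abnormalities, and the post-treatment laboratory shift table, use the worst individual post-dose value through the End of Study or Early Termination visit about 30 days after the last dose, visit window included. Repeat, unscheduled, infusion-reaction and Early Termination assessments all contribute.*

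Naming the visit window matters because the closing visit may fall on Day 31 or 32. The denominator for each count should be stated alongside.

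The cost is one or two sentences and a programming flag; no new data are needed. Abnormality rates may come out slightly higher, and subjects tested more often have more chances to be counted, which a footnote can say.
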